9.2.3. Safety Evaluations

Any clinically relevant changes must be recorded in the eCRF.

Any clinically significant abnormalities, including abnormalities persisting at the end of the study or at early withdrawal, will be followed by the investigator until resolution or a clinically stable endpoint is reached.

The study includes the following evaluations of safety and reactogenicity on timepoints provided in the [Schedule of Activities](#).

9.2.3.1. Adverse Events

All AEs will be reported as specified in Section 12, Adverse Event Reporting. All SAEs will be collected until the end of the double-blind phase; only SAEs related to study vaccine, study procedures, or non-investigational (concomitant) Janssen products, and all AEs leading to discontinuation will be collected during the long-term follow-up phase (Groups 14-15 in Cohort 2).

Unsolicited AEs

Unsolicited AEs will be reported by the participant from the time of each vaccination through the following 28 days, or early discontinuation.^a Relatedness of the AEs should be determined by the investigator. Additionally, AEs that are related to the study procedures or to non-investigational (concomitant) Janssen products will be reported from ICF signature onwards.

Solicited AEs

Information related to solicited AEs defined below, will be recorded by participants in a diary for 7 days after each vaccination. Each participant will be provided with a diary and instructions on how to complete the diary (Section 9.1.1). There will be a minimum 30-minute post-vaccination assessment of solicited events at the site. Diary information will be transcribed by the study-site personnel in the appropriate diary pages of the eCRF. Once a solicited symptom from a diary is considered to be of severity Grade 1 or above, it will be referred to as a solicited AE.

Injection Site (Local) Adverse Events

Participants will be asked to note in the diary occurrences of pain/tenderness, induration/swelling and erythema at the vaccine injection site daily for 7 days post-vaccination. The extent (ie, largest diameter) of any erythema and induration/swelling should be measured (using the ruler supplied), graded (using the functional scale) and recorded daily.

- **Injection Site Pain/Tenderness**

Injection site pain (eg, stinging, burning) is an unpleasant sensory and emotional experience associated with actual or potential tissue damage and occurring at the immunization site (with or without involvement of surrounding tissue). Injection site tenderness is a painful sensation localized at the injection site upon palpation or movement of the limb. Due to the subjective nature of the reaction, the severity assessment of pain/tenderness is self-reported (if a participant is unable to provide self-report, other reporters include a healthcare provider or caregiver).¹⁰

- **Injection Site Erythema**

Injection site erythema is a redness of the skin caused by dilatation and congestion of the capillaries localized at the injection site. It can best be described by looking and measuring.

- **Injection Site Swelling/Induration**

Injection site swelling is a visible enlargement of an injected limb. It may be soft (typically) or firm (less typical). Injection site induration is a palpable thickening, firmness, or hardening of soft tissue, usually has well-demarcated palpable borders, can be visible (raised or sunken compared to surrounding skin), is often 'woody' to touch, and has a flat shape. As differentiation between swelling and induration may be difficult without a healthcare

^a AEs that start more than 28 days after a vaccination, but that are still present at the time of the next vaccination will also be recorded.

professional's assessment, both symptoms have been combined to allow self-assessment by the participants. Swelling and induration can best be described by looking and measuring.

Note: Any other injection site events not meeting the above case definitions should be reported separately as unsolicited AEs.^{22,23}

Systemic Adverse Events

Participants will be instructed on how to record daily body temperature using the thermometer provided for home use. Participants should record the temperature in the diary in the evening of each day of vaccination, and then daily for the next 7 days approximately at the same time each day.^a If more than 1 measurement is made on any given day, the highest temperature of that day will be used in the eCRF.

Fever is defined as an endogenous elevation of body temperature ≥ 38.0 °C, as recorded in at least one measurement.²⁶

In addition to fever, participants will be instructed on how to record daily in the diary for 7 days after each vaccination symptoms of the following events: fatigue, headache, myalgia, arthralgia, chills, and nausea. Severity of these event will be graded by the investigator according to the criteria presented in Section 12.1.3.

If a solicited local or solicited systemic AE is not resolved by 7 days after the vaccination, the follow-up will be captured on the diary. The participant will be instructed to record the date of last symptoms and maximum severity in the diary after resolution.

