- Solicited local AEs: erythema (measured using the ruler supplied), swelling/induration (measured using the ruler supplied and graded using the functional scale), and pain/tenderness.
- Solicited systemic AEs: fatigue, headache, myalgia, arthralgia, chills, nausea, and fever (ie, body temperature ≥ 38.0 °C).

Body temperature (oral route preferred) should be measured at approximately the same time each day, preferably in the evening, using the thermometer supplied. All diary assessments, including body temperature, 7 days after each vaccination may be collected earlier in the day to coincide with the clinic visit.

Unsolicited AEs will be collected for 28 days after each vaccination (ie, from the time of each vaccination through the following 28 days).^a SAEs will be collected from first dose administration to the end of the double-blind phase of the study. During the long-term follow-up phase (Groups 14 and 15 from Cohort 2), only SAEs related to study vaccine, study procedures, or non-investigational (concomitant) Janssen products, and all AEs leading to discontinuation will be collected. All AEs, including any that are ongoing at 28 days after each dose, will be followed until clinical resolution or stabilization. Concomitant medications will be collected from the time of each vaccination, through 28 days after each vaccination, and additionally outside these periods when associated with any SAE. During the long-term follow-up phase (Groups 14 and 15 from Cohort 2), only medications in conjunction with SAEs related to study vaccine, study procedures, or non-investigational (concomitant) Janssen products, or in conjunction with AEs leading to discontinuation should be recorded.

All SAEs and AEs leading to discontinuation from the study/vaccination (regardless of the causal relationship) are to be reported from the moment of first vaccination until completion of the participant's last study-related procedure, which may include contact for safety follow-up.

^a AEs that start more than 28 days after a vaccination, but that are still present at the time of the next vaccination will also be recorded.

STATISTICAL METHODS

Sample Size Determination

For Cohort 1, no formal sample size calculations are done.

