12.1.3. Severity Criteria

All AEs and laboratory data reported as AEs will be coded for severity using the toxicity grading table in [Attachment 1](#). *Note:* Laboratory values within central laboratory normal ranges (even if within a toxicity grade range), or laboratory values outside normal ranges that are not clinically significant in the judgment of the investigator, should not be recorded as AEs.

For AEs not identified in the toxicity grading table, the following guidelines will be applied:

Mild (Grade 1):	Awareness of symptoms that are easily tolerated, causing minimal discomfort and not interfering with everyday activities.
Moderate (Grade 2):	Sufficient discomfort is present to cause interference with normal activity.
Severe (Grade 3):	Extreme distress, causing significant impairment of functioning or incapacitation. Prevents normal everyday activities.
Potentially life-threatening (Grade 4):	Symptoms causing inability to perform basic self-care functions, OR Medical or operative intervention indicated to prevent permanent impairment, persistent disability.

The investigator should use clinical judgment in assessing the severity of events not directly experienced by the participant (eg, laboratory abnormalities).

The toxicity grading scale used for laboratory assessments is based on the FDA toxicity grading table (see [Attachment 1](#)), consistent with the assessment grading used throughout the protocol. If a laboratory value falls within the grading as specified in the FDA table, but also within the laboratory normal limits, the value is considered as normal. For hemoglobin, both the actual value and the change from reference will be graded.

The severity of solicited AEs will be graded in the diary by the participant based on the severity assessment provided in the diary and then verified by the investigator using the FDA toxicity grading table (see [Attachment 1](#)).

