Attachment 1: Toxicity Tables

Adapted from the FDA Guidance document “Toxicity Grading Scale for Healthy Adult and Adolescent Volunteers Enrolled in Preventive Vaccine Clinical Trials” (September 2007).

A: Tables for Clinical Abnormalities

Local Reaction to Injectable Product	Mild (Grade 1)	Moderate (Grade 2)	Severe (Grade 3)	Potentially Life-threatening (Grade 4)
Pain	Does not interfere with activity	Repeated use of non-narcotic pain reliever > 24 hours or interferes with activity	Any use of narcotic pain reliever or prevents daily activity	Emergency room (ER) visit or hospitalization
Tenderness	Mild discomfort to Touch	Discomfort with Movement	Significant discomfort at rest	ER visit or Hospitalization
Erythema/redness*	2.5 – 5 cm	5.1 – 10 cm	> 10 cm	Necrosis or exfoliative dermatitis
Induration/swelling**	2.5 – 5 cm and does not interfere with activity	5.1 – 10 cm or interferes with activity	> 10 cm or prevents daily activity	Necrosis

* In addition to grading the measured local reaction at the greatest single diameter, the measurement should be recorded as a continuous variable.

** Induration/Swelling should be evaluated and graded using the functional scale as well as the actual measurement.

Vital Signs *	Mild (Grade 1)	Moderate (Grade 2)	Severe (Grade 3)	Potentially Life-threatening (Grade 4)
Fever** (°C)	38.0 – 38.4	38.5 – 38.9	39.0 – 40	> 40
Fever** (°F)	100.4 – 101.1	101.2 – 102.0	102.1 – 104	> 104
Tachycardia - beats per minute	101 – 115	116 – 130	> 130	ER visit or hospitalization for arrhythmia
Bradycardia - beats per minute***	50 – 54	45 – 49	< 45	ER visit or hospitalization for arrhythmia
Hypertension (systolic) - mm Hg****	141 – 150	151 – 160	> 160	ER visit or hospitalization for malignant hypertension
Hypertension (diastolic) - mm Hg	91 – 95	96 – 100	> 100	ER visit or hospitalization for malignant hypertension
Hypotension (systolic) - mm Hg	85 – 89	80 – 84	< 80	ER visit or hospitalization for hypotensive shock
Respiratory rate - breaths per minute	17 – 20	21 – 25	> 25	Intubation

* Participant should be at rest for all vital sign measurements.

** Oral body temperature; no recent hot or cold beverages or smoking.

*** When resting heart rate is between 60 and 100 beats per minute. Use clinical judgment when characterizing bradycardia among some healthy participant populations, for example, conditioned athletes.

**** Revised by the sponsor.

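### Protocol 9.2.3.1 has redness and swelling graded on a functional scale, contrary to Attachment 1, and the SAP analyses the recorded grades without re-deriving them from the diameters

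*Protocol*

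**What the plan says.** The protocol describes the grading of local reactions in four places.

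- **Section 9.2.3.1 (Injection Site Adverse Events)** covers erythema and swelling in one sentence: the extent of "any erythema and induration/swelling should be measured (using the ruler supplied), graded (using the functional scale) and recorded daily".
- **Synopsis, Safety Evaluations** lists "erythema (measured using the ruler supplied), swelling/induration (measured using the ruler supplied and graded using the functional scale), and pain/tenderness". Here the functional scale belongs to swelling only, and it is the only grading basis named for swelling.
- **Attachment 1, local-reaction table**, grades erythema at 2.5–5 cm, 5.1–10 cm and over 10 cm for Grades 1 to 3, with Grade 4 defined as "Necrosis or exfoliative dermatitis". The erythema footnote reads "In addition to grading the measured local reaction at the greatest single diameter, the measurement should be recorded as a continuous variable". The swelling footnote reads "Induration/Swelling should be evaluated and graded using the functional scale as well as the actual measurement".
- **Section 12.1.3** codes all AEs with the Attachment 1 table. For solicited events it adds: "The severity of solicited AEs will be graded in the diary by the participant based on the severity assessment provided in the diary", followed by investigator verification against that table.

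SAP 5.1.1 builds solicited AEs from the diary and on-site assessment pages. SAP Attachment 2 assigns each event its maximum grade over the reporting period. SAP 5.1.2 tabulates solicited AEs by worst grade and for Grade 3.

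**The concern.** Solicited local AEs are part of the primary safety endpoint in all three cohorts. Under Protocol 9.2.3.1 and SAP 5.1.1 a reaction counts as an AE only from Grade 1, so the scale bears on incidence as well as severity. The instruction closest to the participant names a scale that Attachment 1 does not provide for erythema and treats as only half of the grade for swelling. If the diary follows that instruction, its grades need not match the table used to interpret them.

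There is also an operational consequence. Section 12.1.2 treats solicited local AEs as related by definition, and Section 11.9 requires notification within 24 hours of any related AE of Grade 3 or above. An under-graded reaction might not prompt that notice.

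**Working it through.** The plan gives no figure to reproduce, so the check compares the texts and then follows a grade through to the tables.

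**Step 1: grading basis by location.**

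| Place | Erythema | Induration/swelling |
|---|---|---|
| 9.2.3.1 | measured; graded on function | measured; graded on function |
| Synopsis | measured | measured; graded on function |
| Attachment 1 | Grades 1–3 by diameter; no activity wording | diameter and function |
| 12.1.3 | Attachment 1 | Attachment 1 |

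For erythema, 9.2.3.1 stands alone against the other three. For swelling, both 9.2.3.1 and the synopsis leave out the diameter part of the grade.

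**Step 2: does the difference change a grade?** For swelling it can be shown directly, because Attachment 1 contains functional criteria. Its row requires 2.5–5 cm *and* no interference for Grade 1, 5.1–10 cm *or* interference for Grade 2, and over 10 cm *or* prevention of daily activity for Grade 3. For swelling that does not interfere with activity:

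- 12 cm: Grade 3 by Attachment 1, because the diameter exceeds 10 cm. On function alone neither the Grade 2 nor the Grade 3 criterion is met, so the grade is below 2.
- 7 cm: Grade 2 by Attachment 1; below Grade 2 on function alone.
- 1.5 cm: below Grade 1 by Attachment 1, hence not an AE. It would become a Grade 1 AE only if the diary gives Grade 1 to any non-interfering swelling, which is an assumption about a form that is not shown.

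Because Grades 2 and 3 are joined by *or*, dropping the diameter can only lower a swelling grade at those levels.

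For erythema no comparison can be computed. The documents contain no functional scale for redness, so there is nothing to set against the diameter grade.

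**Step 3: is the recorded grade corrected before analysis?**

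- Section 9.1.1 says the diary carries its own grading scales, and 12.1.3 has the participant grade from them.
- Sections 9.2.3.1, 12.3.1 and 17.4 have diary information transcribed into the eCRF. Section 17.4 treats the diary as source data.
- Section 12.1.3 calls for verification but does not say that an Attachment 1 grade replaces a discordant diary grade.
- SAP Attachment 2 carries the maximum recorded grade forward. No step uses the diameter.
- By contrast, SAP 5.2 and 5.3 grade laboratory values and vital signs from the measurements, and SAP Attachment 1 prints those tables. It prints none for local reactions.

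Investigator verification is therefore the only safeguard, and the analysis has no second check.

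**The case against.** The strongest reply is that the governing scale is already named. Section 9.2.3.1 refers AE reporting to Section 12, and 12.1.3 makes Attachment 1 the table for both coding and verification. The sentence in 9.2.3.1 reads like two symptoms compressed into one clause. The same section says erythema is best described by looking and measuring, and the synopsis does not attach the functional scale to it. Diameters are recorded in any case, the safety analysis is descriptive, and pausing rules 3 and 4 do not cover solicited local events.

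Most of this stands. It rules out several stronger readings that a reader might infer:

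- *That the grade and AE status of redness are left open.* They are not; 12.1.3 points to Attachment 1.
- *That specific erythema grades by function can be set against the diameter grades.* They cannot without borrowing the activity wording of the swelling row, which no passage instructs.
- *That erythema is graded only by diameter.* Grade 4 is not.
- *That every vaccination in the study is affected.* Only reactions whose two grades differ could be.
- *That the protocol disagrees on who grades systemic events.* Section 9.2.3.1 says "Severity of these event will be graded by the investigator according to the criteria presented in Section 12.1.3", and 12.1.3 describes a participant grade followed by investigator verification. That is mostly a cross-reference and needs only a wording alignment.

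What the reply does not answer is Step 3. Naming the right table does not ensure that the transcribed grade conforms to it, and an operative instruction to participants on a primary endpoint should not contradict that table.

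**Conclusion.** The contradiction is real and its consequence is limited. Attachment 1 is the intended scale. Section 9.2.3.1 departs from it for erythema and, together with the synopsis, states only part of it for swelling. The SAP neither restates the local-reaction table nor recalculates the grade. The firmest instance is large swelling without interference, which could drop out of the Grade 3 table.

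This rests on two conditions that the documents do not settle: that the diary scale follows 9.2.3.1, and that verification does not correct the transcribed grade. If the diary already reproduces Attachment 1, there is no effect on the data and only the wording needs repair. The number of misgraded reactions cannot be estimated, and the documents give no basis for saying how often redness or swelling interferes with activity. No hypothesis test is affected.

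**What to change.** 1. **Protocol 9.2.3.1 and synopsis.** Split the sentence so that erythema is graded by largest diameter and induration/swelling by diameter and function, both as set out in Attachment 1 and applied through Section 12.1.3. In the same edit, align the sentence on who grades systemic events with 12.1.3.
2. **SAP 5.1.1 and Attachments 1 and 2.** Add the local-reaction table. State that the analysed erythema grade (Grades 1 to 3) and the diameter component of the swelling grade are derived from the recorded diameters using the Attachment 1 thresholds. The functional component and Grade 4 stay as recorded. Apply the derivation to the daily records before they are collapsed to one record per event.
3. **Stated limit.** For reactions lasting beyond the 7-day diary period, 9.2.3.1 asks only for the last symptom date and maximum severity. Say that the recorded grade is used where no diameter exists.

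The cost is a few sentences in each document and one programmed derivation. No new data are needed for the diary days, since both diameters are already recorded daily, and the SAP part can still be done after data collection.

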For any clinically significant abnormal laboratory value that has increased in grade over baseline, the test must be repeated at the next scheduled visit or sooner based on investigator’s judgment, however Grade 3 and above abnormalities should be retested within 48 hours. Any clinically significant abnormalities (including those persisting at the end of the study or early withdrawal) will be followed by the investigator until resolution or a clinically stable endpoint is reached.

Screening Procedures (Cohorts 1 and 2 Only)

For entry into the study, each participant must be healthy on the basis of clinical laboratory tests performed at screening. Enrollment of a participant with clinical laboratory values outside of the central laboratory normal range representing FDA toxicity Grade 2 is allowed if the investigator considers the values reasonable for the population under study and not clinically significant.

Additional clinical laboratory assessments to be performed at screening include serology testing (HIV type 1 or type 2, hepatitis B, hepatitis C).

9.2.3.3. Electrocardiogram

In Cohorts 1 and 2, supine 12-lead ECGs will be performed at screening and interpreted locally; ECGs will only be performed thereafter during the study if clinically indicated based on signs and symptoms.

For 30 minutes prior to the ECG, participants should refrain from meals, hot or cold beverages and strenuous exercise, and should remain in a room with a comfortable temperature. Each ECG should be obtained after the participant has been at rest for at least 5 minutes.

Enrollment of a participant is allowed even with abnormal ECG results as long as the investigator feels that these are not clinically significant and appropriate for the population.

9.2.3.4. Vital Signs

Blood pressure and pulse/heart rate measurements should be preceded by at least 5 minutes of rest in a quiet setting without distractions (eg, television, cell phones).

Vital signs are to be measured before blood draws and nasal samples.

The following measurements will be performed:

- Heart rate (beats per minutes), respiratory rate (breaths per minute), supine systolic blood pressure (mmHg) and supine diastolic blood pressure (mmHg)
- Body temperature (oral route preferred, or in accordance with the local standard of care)

Confirmatory vital signs measurement can be done if inconsistent with a prior measurement. If any clinically significant changes in vital signs are observed, they will be reported as an AE and followed to resolution, or until reaching a clinically stable endpoint.

9.2.3.5. Physical Examination

A full physical examination, including height and body weight, will be carried out at screening and before the Month 12 booster (Cohorts 1 and 3) and before the Month 24 booster (Cohort 3 only). At all other visits, an abbreviated, symptom-directed examination will be performed by the investigator based on clinically relevant issues, clinically relevant symptoms and medical history. Symptom-directed physical examination may be repeated if deemed necessary by the investigator.

Physical examinations will be performed by the investigator or an appropriately trained delegate. Any clinically relevant abnormalities or changes in severity observed during the review of body systems should be documented in the eCRF as an AE.

